1.1 Background

Acne Vulgaris

Acne is a disease that affects almost 100% of the population, from ages 8 to 80. The symptoms range from rare, mild disease to severe, disfiguring disease, resulting in scarring. The more severe the disease, the higher the incidence of depression, even to the extent of suicidal thoughts. The clinical presentation ranges from comedonal disease (whiteheads and blackheads or “little bumps”), to red papules and large cysts (“big bumps”). Scarring is associated with cysts and “big bumps,” as well as scratching, picking, or popping of lesions. The scarring can be extremely disfiguring. Adolescents with acne suffer greatly from their disease, affecting their social and academic growth. The cause is essentially unknown.

Most authorities agree that there is a genetic blueprint for the duration and severity of acne, which varies greatly from patient to patient. There is no ethnic predilection, but males are generally more severely affected since testosterone is an aggravating factor. The transition into puberty causes an increase in the size of sebaceous (oil) glands, as well as increased oil secretion. These changes, as well as a change in the keratinization of the hair follicle, cause occlusion, which results in comedone (whitehead and blackhead) formation. This occlusion allows the proliferation of *Propionibacterium Acnes* bacteria. This bacteria is felt to be the cause of larger acne lesions due to the immune system response to the bacteria, inflammatory enzymes produced by the bacteria, or both. Some feel the depth of the occlusion in the hair follicle determines the size of the resultant acne lesion, with a deeper occlusion resulting in a larger lesion. External factors vary from patient to patient. Stress is a universal aggravating factor. With the exception of dairy products in women, dietary triggers are more individual than universal (otherwise there would be no acne as no one would eat the offending trigger). Cosmetics generally do not play a role; however, thick theatrical make-up, as well as general cosmetics while sweating can aggravate the disease. Hair spray, hair oil, and mousse can aggravate the condition as can hats, sweat bands, and long hair (bangs as well as shoulder length). Some feel acne improves in the summer, either due to lack of stress or increased sun exposure¹.

In acne, blue light acts on chemicals called porphyrins². It is known that *P. acnes* produce porphyrins during their normal life cycle, as part of their normal metabolism process. *P. acnes* is capable of producing high amounts of endogenous porphyrins in the absence of any trigger molecules³.

Intense Pulsed Light (IPL)

Intense Pulsed Light (IPL) technology uses light pulses delivered by a flashlamp with high peak power and short pulses. The light is directed by a reflector and then transmitted through various filters that cut off the lower wavelength range of the emitted light; therefore, only those wavelengths longer than that of the filters are transmitted. Applying the physical principle of selective photothermolysis, IPL is used for performing various skin treatments (acne vulgaris, scars, striae, etc.) as well as for eliminating unwanted hair, benign vascular/pigmented lesions and unwanted leg veins^{4,5}.

Photo-biological Principles in Acne Treatment

A molecule that is absorbed in the skin is named a chromophore. Each and every photo-biological process starts in absorption of light energy by a selected chromophore. Every chromophore has a specific absorption spectrum of its own. After absorption, the chromophore is transformed from its stable state to the excited state. This unstable condition induces chemical reaction and a photoproduct. The biochemical changes cause reaction of the skin. In humans, the skin contains chromophores that are photo-dynamically active and photo-instable substances. The Gram-positive microaerophilic skin bacterium *Propionibacterium acnes* is implicated in the pathophysiology of acne vulgaris. As part of its normal metabolism process, *P. acnes* produce porphyrins, mainly protoporphyrin and coproporphyrin-photosensitizers. Photosensitizers are molecules that have the trait of absorbing light energy and using this energy to carry out chemical reactions in cells and the body tissues. Each photosensitizer has its proper wavelength of absorption, usually several, and a wavelength of emission. Excitation of the porphyrins by absorption of light causes the formation of singlet O₂ and reactive radicals. Porphyrins are a ubiquitous class of naturally occurring compounds containing the porphin structure of four pyrrole rings connected by methane bridges in a cyclic configuration, to which a variety of side chains are attached, usually metallated, for example, with iron to form heme. In porphyrin-visible absorption spectra, the highly conjugated aromatic macrocycle shows intense absorption in the neighborhood of 400 nm; the highest peak of light absorption (and sensitizer activation) is called the "Soret Band". It is usually located in the blue and ultraviolet range. Because the highest peak of absorption of porphyrin is at blue light (415 nm), some light source systems use this spectrum for the treatment of acne. Visible spectra of porphyrins also show several weaker absorptions (Q Bands) at longer wavelengths (450 to 700 nm). The efficacy of *P. acnes* photo-inactivation is determined by the rate of production of excited porphyrins molecules. In order to achieve maximum process efficacy, the controlled parameters in this complex photobiological process - concentration of photons, temperature and the wavelength of photons - can be technologically optimized. Most of the existing laser/light-based devices, however, are limited by one of the previously mentioned parameters, which may alter *P. acnes* photo-inactivation efficiency⁶.

Radio-Frequency (RF)

The RF energy is high frequency alternating electrical current that passes into the dermis and hypodermal tissues without disruption of the epidermal-dermal barrier. The high frequency oscillating electrical current results in collisions between charged molecules and ions and the micromolecular mechanical energy from these collisions is transformed into heat^{7,8,9}. This biological RF heat occurs irrespective of chromophore or skin type and is not dependent upon selective photothermolysis.

Radio-Frequency (RF) biological Principles in Acne Treatment

The RF heat has different biological and hence, clinical effects, depending upon the tissue targeted. In the dermis, where the primary cellular element is the fibroblast and the extracellular matrix (ECM) is comprised of collagen, elastin and ground substances, the RF mediated thermal stimulation of the ECM results in an immediate and temporary **shrinkage of the collagen** triple helix^{7,8,9}. Further, the RF thermal stimulation results in a micro-inflammatory stimulation of the fibroblast which in response produces new collagen (**neocollagenesis**) and new elastin (**neaelastogenesis**), and ground substances^{8,9}. **This modality is said to also target the sebaceous gland, an important part in the pathogenesis of acne, by causing shrinkage and decreasing sebum output**¹⁰. Studies have shown that pore size is associated with high sebum output level

(seborrhea), aging, sex, genetic predisposition, chronic ultraviolet light exposure, and vitamin A deficiency. Previous studies have indicated that enlarged pores are attributable to skin aging caused by changes in the dermal matrix. In skin aging, photo-aging, one of the most important extrinsic factors, changes dermal thickness and disorients the dermal matrix, including collagen and elastin, by upregulating the matrix metalloproteinases. It has been suggested that large pore size is more significantly associated with increased sebum output level than with sex or age. Excessive sebum excretion has been also accepted as one of the most important etiological factors in acne vulgaris and patients with acne tend to have enlarged facial pores¹¹. Lee et al. demonstrated a positive therapeutic effect of FRM (Fractional Radiofrequency Microneedle) on inflammatory acne vulgaris and related scars after two sessions. The authors suggested that FRM might have a thermal inhibitory effect on sebaceous gland, but objective data regarding sebum excretion were lacking¹⁰.

1.2 Rationale for the Study

The AC DUAL Intense Pulsed Light (IPL) applicator is indicated for the treatment of Acne Vulgaris. It uses a blue light (415 nm) to target the porphyrins produced by the P. Acne bacteria and destroy the bacteria, and also uses a red light (630 nm) to help reduce inflammation, inhibit sebum production and improve healing. This study is intended to evaluate the effect of IPL treatment on Acne Vulgaris.

The study hypothesis is that the use of the AC DUAL applicator combined with the Diamondpolar applicator will improve the appearance of Acne Vulgaris by at least 2 points on the Global Acne Assessment Score (GAAS) at 6 weeks follow-up compared to baseline in the study population and in addition, as a secondary success criteria, reduction of 25-50% of inflammatory lesions and non-inflammatory lesions. The combination treatment will also be compared to IPL treatment alone as a secondary endpoint.

2 The Investigational Device

The Venus Versa system is a multi-application device consist of a console and 10 detachable handpieces, or applicators. The Versa Console supports 3 types of energies: 1) IPL; 2) RF; 3) Magnetic Pulse (MP)². The detachable handpieces are operating via either IPL, fractional RF or a combination of RF with Magnetic Pulse (MP)².

IPL Based applicators: HR650, HR690, SR515, SR580, HR650XL, HR690XL, AC DUAL.

Fractional RF Based applicator: Viva.

RF and Magnetic Pulse (MP)² Based applicators: Diamondpolar, Octipolar.

The IPL applicators deliver optical energy in the form of Intense Pulsed Light to the patient skin. The intense pulsed light lamp delivers non-coherent light distributed over a range of wavelengths from 500 nm to 1200 nm. Different filters are embedded in the different applicators so that each applicator can deliver the desired spectrum according to the indications to be treated.

The energy delivered to the patient's skin is used to treat various conditions via the mechanism of selective photothermolysis. The selective absorption of different wavelengths by the skin and its components (e.g., blood vessels, hair follicles, etc.) lead to localized heating and thermal lysis of the anatomic target. The different applicator uses optical filters to optimize the energy delivered to the body, and match the spectrum of light delivered to the intended clinical application.

2.1 Venus Versa module

The Venus Versa system is designed to deliver optical energy to the skin via various applicators connected to the console. Each applicator delivers different wavelengths of the same Intense Pulsed Light source. The device provides individual adjustment of light fluency and pulse duration as appropriate for each patient. The applicator has integrated skin cooling to enhance safety and comfort of the treatment.

The Venus Versa system consists of a low voltage power supply (LVPS) unit, a capacitor charger, capacitors bank, switching module, water cooling system, controller and user interface, including a touch-screen LCD display.

2.2 AC DUAL applicator

The applicator is connected to the console via cables. It comprises an IPL source, a filter (designed to filter light in the optimal bands of the spectrum for specific treatments) and a cooled light-guide (sapphire) that contacts the patient's skin.

The IPL applicator operates a blue light (415 nm) and also red light (630 nm) simultaneously. The IPL applicator also includes a sapphire cooled light guide of 10x30mm. The system controls the pulse shape and fluence.

2.3 (MP)² Diamondpolar applicator

The Diamondpolar applicator of the Venus Versa system, has 4 electrodes. Each electrode and its surrounding coil simultaneously emit RF and Pulsed Magnetic Field. The RF current is produced between any two electrodes in the array by rapidly alternating RF current between the different electrodes; the device raises the temperature of the treatment area homogeneously, without the RF focal "hot spots" seen with other RF devices.

3 Study Design

This is a prospective, open label clinical trial before-after study design. This study is designed to evaluate the safety and efficacy of the Venus Versa Diamondpolar applicator followed by AC DUAL applicator and the AC DUAL applicator alone in treating mild to moderate acne vulgaris.

This study will include up to 6 visits at the clinic: initial screening/consultation, 4 treatments (Tx) visits at 1 week intervals, and 1 follow-up (FU) visit at 6 weeks after the last treatment visit.

Up to 50 healthy subjects, age 18 to 55 years of age with mild to moderate acne vulgaris, defined as at least 10 inflammatory and 15 non-inflammatory lesions, with no odulocystic lesions will be enrolled. Subjects must meet the eligibility criteria detailed in the protocol and sign the informed consent form prior to any study

procedure. At the first treatment visit, the investigator will collect demographic and medical information and perform 3 test spots to evaluate skin sensitivity and choose appropriate presets. Subjects with skin type IV-V will be monitored 48-96 hours after the test spot for their skin reaction. Subjects that demonstrate excessive skin reaction to the test spot will be withdrawn from the study and will not be included in the study efficacy population or in the safety analysis since study treatment has not occurred. Should a subject (or the subject's legally authorized representative) decide to voluntarily withdraw, all efforts will be made to collect and report the final visit observations, and the reasons for withdrawal, as thoroughly and timely as possible. Withdrawals will be documented in the CRF and reported to local institutional review board (IRB) or ethical committees as required. The first treatment visit may occur on the same day as the screening visit but can be scheduled up to 30 days after the screening.

The duration of the treatment session will be approximately 40 minutes depending on the treated area size. Expected immediate response includes temporary mild to moderate erythema and/or edema. Skin safety assessments will be conducted by the investigator after each treatment session and at follow-up visits. Photography will be conducted at baseline, the beginning of last visit and at FU. The level of the subject's discomfort will be documented at the end of each treatment session. Subject satisfaction will be evaluated at FU. Evaluation by up to 3 independent reviewers will be based on before/after pictures of the baseline, before the last treatment and at the 6 week follow up visit using GAAS.

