3.3 Safety

- Safety will be evaluated based on the number and type of any adverse event recorded throughout the study. Adverse events will be reported and categorized based on severity and device-relatedness. In addition, immediate response following treatment associated with various settings (e.g., erythema, edema, purpura, etc.), although expected results of treatment that are not considered adverse events, will be collected and reported for purposes of completeness. Information will also be captured on the intensity of response and the time required for resolution.

3.4 Study duration:

Duration of subject's participation: Up to 11 weeks from enrollment to termination (see Figure 1).

Study duration for entire study sample: Estimated to be 16 months from enrollment of first subject to the termination of the last. This is based on estimate of 8 months for recruitment + 2 months subject participation + 1 months collecting data.

Figure 1: Subject Participation

Time Intervals		1 week	1 week	1 week	1 week	6 weeks
	Enrollment	Treatment 1	Treatment 2	Treatment 3	Treatment 4	Follow-up
Timeline	Screening	Week 1	Week 2	Week 3	Week 4	Week 10

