3.5 Schedule of Times and Events

The following table provides a summary of the required study visits and the procedures and assessments to be performed at each visit. Details of the procedures and assessments will be described subsequently in the protocol.

Table 1: Study Procedures - CS2715

Tx=Treatment; FU=Follow Up

Visit#	Visit #1	Visit #2	Visit #3	Visit #4	Visit #5	Visit #6
Study Activities	Screening & Test spot	Tx1	Tx2	Tx3	Tx4	FU
Timing (see Figure 1)		0-7 days post given ICF	1 week + 5 days post 1 st TX	2 weeks + 5 days post 1 st TX	3 weeks + 5 days post 1 st TX	6 weeks + 7 days after last Tx
Informed Consent	X					
Eligibility assessment	X					
Demographic information	X					
Medical/surgical history	X					
Physical examination	X					
Urine pregnancy test	X					X
Test spots	X					
Photographs		X			X	X
Lesion Count (FACE)	X	X	X	X	X	X
Treatment		X	X	X	X	
Immediate/short term response		X	X	X	X	
Subjects discomfort assessment (VAS)		X	X	X	X	
Subject improvement evaluation using GAIS						X
Subject satisfaction assessment scale (5-point Likert scale)						X
Subject improvement assessment of "quality of life" using QOL Questionnaire	X		X	X	X	X
Independent reviewer improvement evaluation using GAAS						X
Adverse events		X	X	X	X	X
Concomitant medications		X	X	X	X	X

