4.2.1 Inclusion Criteria

Subjects must meet all of the following inclusion criteria to be entered into the study:

1. Able to read, understand and provide written Informed Consent;
2. Healthy adult, male or female, 18-55 years of age with Fitzpatrick-Goldman skin type I-VI.
3. Having mild to moderate acne vulgaris with at least 10 inflammatory and 15 non-inflammatory lesions, but no nodulocystic lesions.
4. Able and willing to comply with the treatment/follow-up schedule and requirements;
5. Women of child-bearing age are required to be using a reliable method of birth control (such as an intrauterine device, birth control pills, condom with spermicidal, Nuvaring, partner with vasectomy or abstinence) at least 3 months prior to enrollment and throughout the course of the study.
6. Negative urine pregnancy test.
7. Able to tolerate the treatment as determined by a test application.
8. Willing to avoid direct sunlight and willing to use topical sunscreen for the duration of the study

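### Subjects withdrawn for an excessive test-spot reaction are left out of the safety analysis, so any adverse event from that device exposure is missing from the analysed safety results

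*Combined protocol and SAP*

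**What the plan says.** Section 3 (Study Design) withdraws subjects who react excessively to the test spot and states that they "will not be included in the study efficacy population or in the safety analysis since study treatment has not occurred". The same section says "Subjects must meet the eligibility criteria detailed in the protocol and sign the informed consent form prior to any study" procedure, so consent comes before the test spot. It also says of withdrawals in general: "Withdrawals will be documented in the CRF".

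Section 3.3 defines the safety endpoint as the "number and type of any adverse event recorded throughout the study" and makes no exception for test spots. Section 5.1.3 describes the test spot: up to three spots, starting at a low output and adjusted upwards, with the stated purposes of checking for side effects and choosing settings. Section 7.4 names one analysis set, guided by intent-to-treat for enrolled subjects, and defines no separate safety set.

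The documents differ on when the test spot takes place. Section 3 says "At the first treatment visit, the investigator will collect demographic and medical information and perform 3 test spots". Table 1 in section 3.5 puts it at visit 1, headed "Screening & Test spot". Section 5.1.3 places it before enrolment, and inclusion criterion 7 in section 4.2.1 reads "Able to tolerate the treatment as determined by a test application".

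**The concern.** That study treatment has not occurred is a good reason to leave these subjects out of the efficacy population. It is not a reason to leave them out of safety. They consented, received device energy, and are removed because of how their skin responded to it. An exclusion that depends on the safety outcome takes out the subjects most likely to have a device-related event.

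Safety is a stated aim of this pilot (sections 3 and 7.3), and the endpoint is a count and listing of AEs. If k of the excluded reactions are AEs, the analysed count is short by k and their type is not shown.

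**Working it through.** The plan gives no figure on this point, so there is none to reproduce. The check is mainly textual.

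**Setting the sections side by side**

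1. *Exposure.* Section 5.1.3 makes the test spot a device application used to detect side effects. Section 3 requires consent first. The subject is consented and exposed.
2. *Endpoint.* Section 3.3 covers all recorded AEs over the whole study. The exclusion in section 3 conflicts with this, and no other section returns these subjects to the safety summaries.
3. *Individual reporting.* Section 8.1.5 requires anticipated AEs during or after use of the device to be reported to the sponsor; its list includes irritation, blistering and burns. Section 8.2.1 requires all serious AEs to be reported to the monitor. These routes cover a test spot, but they are not the safety analysis.
4. *Recording.* As the table reads in the text available, the AE row of Table 1 has five marks, fitting visits 2 to 6, and the immediate-response row has four, fitting visits 2 to 5. Neither appears to cover visit 1, where the test spot sits. The definition in section 8.1 covers events at any point in the study, but its recording sentence refers to events during or after treatment with the device, and section 3 says a test spot is not study treatment. A minor event that is neither anticipated nor serious may therefore go unrecorded. The withdrawal and its reason are still recorded (sections 3 and 4.3).

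**Illustration of size**

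Input from the documents: up to 50 subjects (section 7.3). The rate of excessive reactions is not given; every rate and count below is an assumption.

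The chance that the rule removes at least one of 50 subjects is 1 − (1 − p)^50:

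- p = 1%: 1 − 0.99^50 = 39.5%
- p = 2%: 1 − 0.98^50 = 63.6%
- p = 5%: 1 − 0.95^50 = 92.3%

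Suppose k reactors each have an AE. The plan's safety analysis shows none of these events. A table over all test-spotted subjects would show the following, with exact (Clopper-Pearson) 95% intervals:

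| k | Reactors within the 50 | 50 treated plus k reactors |
|---|---|---|
| 0 | 0/50 (0 to 7.11%) | not affected |
| 1 | 1/50 = 2.0% (0.05 to 10.65%) | 1/51 = 2.0% (0.05 to 10.45%) |
| 3 | 3/50 = 6.0% (1.25 to 16.55%) | 3/53 = 5.7% (1.18 to 15.66%) |
| 5 | 5/50 = 10.0% (3.33 to 21.81%) | 5/55 = 9.1% (3.02 to 19.95%) |

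The middle column treats reactors as withdrawn enrolled subjects (section 3). The right-hand column treats them as not yet enrolled (section 5.1.3). The choice hardly matters.

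**When a pooled rate would be understated**

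With j AEs among r reactors and a AEs among n treated subjects, (a + j)/(n + r) > a/n exactly when j/r > a/n. Take r = 3, a = 5 and n = 47, so a/n = 10.6%:

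- j = 0: 5/50 = 10.0%, which is lower, so nothing was understated
- j = 1: 6/50 = 12.0%
- j = 3: 8/50 = 16.0%

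The rate in treated subjects stays at 5/47 = 10.6% throughout.

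**The case against.** The strongest reply is that these subjects are screen failures. Table 1 puts the test spot at screening, criterion 7 makes tolerance a condition of entry, section 5.1.3 places the test before enrolment, and section 5.2 describes assignment to treatment under the treatment visits. Section 3 is then the outlier, a reactor is never enrolled, and the intent-to-treat wording in section 7.4 does not reach that subject. Restricting a safety set to treated subjects is also a common choice, and the plan gives its reason.

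The screen-failure reading is tenable, and it weakens any argument from section 7.4. It does not rescue the rule: under either reading a consented person was exposed to the device, and an event from that exposure goes unanalysed.

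Three further objections stand as limits on the point:

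- A reader might infer that test-spot AEs are hidden from the sponsor or from all reporting. The documents do not support that, because sections 8.1.5 and 8.2.1 still require individual reports. The gap is in the analysed results.
- A reader might infer a flat contradiction with section 8.1. Its definition is broad, but its recording sentence is tied to treatment with the device and is compatible with section 3. That leaves a gap in coverage and a weaker conflict.
- The effect is conditional. Test spots start at low output behind the ear or on the shoulder, no reaction rate is given, and there may be no reactors.

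**Conclusion.** The point holds and should be fixed. As written, section 3 removes device-exposed subjects from the safety analysis because they reacted to the device, and nothing elsewhere brings their events back. The analysed AE count is short by however many of those reactions are AEs, and minor ones may not be recorded.

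The existence of the exclusion is certain; its size is unknown. The 2.0% to 10.0% range rests on an assumed 1 to 5 events among 50 tested subjects. If no reactor has an AE, nothing is lost. It would be wrong to conclude that the rule biases AE rates by arm, which concern treated subjects and do not change, or that it always lowers an overall rate, which happens only under the condition shown above. The efficacy exclusion is not in question. The reading of Table 1 depends on how its columns line up in the available text.

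**What to change.** 1. In section 3, delete the words that extend the exclusion to the safety analysis. Keep the efficacy exclusion.
2. In section 7.4, define the safety set as every subject exposed to the device, test spot included.
3. In Table 1 and section 8.1, start AE and immediate-response recording at the first test spot.
4. Report test-spot reactions and AEs in a separate table with all test-spotted subjects as the denominator. Keep by-arm AE tables for treated subjects only, and do not pool the two.
5. Reconcile section 3 with sections 3.5, 4.2.1 and 5.1.3 on whether the test spot precedes enrolment.

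Cost: a small protocol and CRF amendment needing ethics approval (section 9.7), one extra table, and possibly a less favourable safety summary. Test-spot reactions are already assessed (section 5.1.3) and withdrawal reasons already recorded (section 4.3). Amendment 2 is dated April 2017 and the projected start was September 2016, so some subjects may already have been tested without visit-1 AE data. The new table should state how many.
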